6.3.14 Diet/Activity/Other Considerations

Diet

Participants should maintain a normal diet unless modifications are required to manage an AE such as diarrhea, nausea or vomiting.

Contraception

Pembrolizumab may have adverse effects on a fetus in utero. Furthermore, it is not known if pembrolizumab has transient adverse effects on the composition of sperm. Non-pregnant, non-breast-feeding women may be enrolled if they are willing to use 2 methods of birth control or are considered highly unlikely to conceive. Highly unlikely to conceive is defined as 1) surgically sterilized, or 2) postmenopausal (a woman who is ≥ 45 years of age and has not had menses for greater than 1 year will be considered postmenopausal), or 3) not heterosexually active for the duration of the study. The two birth control methods can be: two barrier methods or, a barrier method plus a hormonal method, to prevent pregnancy. Participants should start using birth control from study Visit 1 (prescreening visit) throughout the study period up to 120 days after the last dose of pembrolizumab and 180 days after the last dose of cetuximab.

The following are considered adequate barrier methods of contraception: diaphragm, condom (by the partner), copper intrauterine device, sponge, or spermicide. Appropriate hormonal contraceptives will include any registered and marketed contraceptive agent that contains an estrogen and/or a progestational agent (including oral, subcutaneous, intrauterine, or intramuscular agents).

Participants should be informed that taking the study medication may involve unknown risks to the fetus (unborn baby) if pregnancy were to occur during the study. In order to participate in the study they must adhere to the contraception requirement (described above) for the duration of the study and during the follow-up period defined in **Section 8**. If there is any question that a participant will not reliably comply with the requirements for contraception, that participant should not be entered into the study.

Use in Pregnancy

If a participant inadvertently becomes pregnant while on treatment with pembrolizumab, the subject will immediately be removed from the study. The site will contact the subject at least monthly and document the subject's status until the pregnancy has been completed or terminated. The outcome of the pregnancy will be reported to the Sponsor and to Merck without delay and within 24 hours to the Sponsor and within 2 working days to Merck if the outcome is a serious adverse experience (e.g., death, abortion, congenital anomaly, or other disabling or life-threatening complication to the mother or newborn). Refer to **Section 10.4.1**

The study investigator will make every effort to obtain permission to follow the outcome of the pregnancy and report the condition of the fetus or newborn to the Sponsor. If a male subject impregnates his female partner the study personnel at the site must be informed immediately and the pregnancy reported to the Sponsor and to Merck and followed as described above and in Section 10.4.1.

Use in Nursing Women

It is unknown whether pembrolizumab is excreted in human milk. Since many drugs are excreted in human milk, and because of the potential for serious adverse reactions in the nursing infant, subjects who are breast-feeding are not eligible for enrollment.

6.4 Supportive Care Guidelines for Cetuximab

6.4.1 Dermatologic Management and AEs

A regimen of pre-emptive skin care is recommended for all patients on the study, as this has been demonstrated to decrease incidence of dermatologic AEs. They should be advised to continue this plan of care for the initial six weeks, with further continuation at the discretion of the investigator. The following components are to be included:

- Twice daily moisturizers – thick, alcohol free emollients of the patients' choice
- Low potency topical corticosteroid twice daily to face, neck, back, chest – e.g. hydrocortisone 2.5%
- Prophylactic oral antibiotics – e.g. doxycycline 100 mg po bid, minocycline 100 mg daily or acceptable alternative such as cephalexin 500 mg po bid, cefadroxil 500 mg po bid, or trimethoprim-sulfamethoxazole 160-800 mg po bid.
- Broad spectrum sunscreen (UVA/UVB) with SPF \geq 15 applied to sun-exposed areas regularly

Additional recommendations for skin care include:

- Limit excessive sun exposure
- Avoiding lotions, detergents with perfumes
- Reduce the frequency and duration of hot showers, and consider using lukewarm water

For **grade 1 rash**, reinforce skin care measures and consider adding topical antibiotics to skin care: Clindamycin 1% gel, Erythromycin 3% gel or cream, metronidazole 1% cream or equivalent products are recommended.

For **grade 2 rash**, **consider** the addition of a medium to high potency topical corticosteroid to chest/back/extremities: e.g. Fluocinonide 0.05%, hydrocortisone valerate 0.2%.

For **grade 3 rash**, hold cetuximab. If intolerable, consider a short course of oral corticosteroids, prednisone 0.5 mg/kg, to a maximum of 40 mg daily x 7 days.

6.4.2 Hypomagnesemia

Anti-EGFR therapies such as cetuximab have an established link to hypomagnesemia. Magnesium levels are to be monitored and levels replaced on therapy and up to 8 weeks after completion of therapy, as per practice standard.

6.5 Duration of Treatment

Participants may remain on study and continue to receive treatment in the absence of disease progression, unacceptable toxicity and withdrawal from study, intercurrent illness that prevents further administration of treatment, participant demonstrates an inability/refusal to comply with oral medication regime or, participant withdraws from study.

If radiologic imaging by the site identifies PD by RECIST 1.1, subject management and tumor assessment will shift to irRECIST. Consent addendum should be obtained to continue on treatment past progression. Imaging should be repeated ≤ 6 weeks later in order to confirm PD with the option of continuing treatment per below while awaiting radiologic confirmation of progression.

If repeat imaging shows $< 20\%$ tumor burden compared to nadir, stable or improved previous new lesion (if identified as cause for initial PD), and stable/improved non-target disease (if identified as cause for initial PD), PD is not confirmed. Treatment may continue and subsequently follow regular imaging schedule.

If repeat imaging confirms PD (irPD) due to any of the scenarios listed below, subjects will be discontinued from study therapy (exception noted in Section 6.6).

In determining whether or not the tumor burden has increased or decreased, site study team should consider all target lesions as well as non-target lesions.

Scenarios where PD is confirmed at repeat imaging:

- Tumor burden remains $\geq 20\%$ and at least 5 mm absolute increase compared to nadir
- Non-target disease resulting in initial PD is worse (qualitative)
- New lesion resulting in initial PD is worse (qualitative)
- Additional new lesion(s) since last evaluation
- Additional new non-target progression since last evaluation

In subjects who have initial evidence of radiological PD by the site, it is at the discretion of the PI whether to continue a subject on study treatment until repeat imaging is obtained (irRECIST subject management). This clinical judgment decision should be based on the subject's overall clinical condition, including performance status, clinical symptoms, and laboratory data. Subjects may receive study treatment while waiting for confirmation of PD if they are clinically stable as defined by the following criteria:

- Absence of symptoms and signs indicating clinically significant progression of disease, including worsening of laboratory values
- No decline in ECOG performance status
- Absence of rapid progression of disease
- Absence of progressive tumor at critical anatomical sites (e.g., cord compression) requiring urgent alternative medical intervention

When feasible, subjects should not be discontinued until progression is confirmed. This allowance to continue treatment despite initial radiologic progression takes into account the observation that some subjects can have a transient tumor flare in the first few months after the start of immunotherapy, but with subsequent disease response. Subjects that are deemed clinically unstable are not required to have repeat imaging for confirmation of PD.

6.6 Treatment Discontinuation

Upon treatment discontinuation all end of treatment evaluations and tests will be conducted. All participants who discontinue due to an AE must be followed until the event resolves or stabilizes. Appropriate medical care should be provided until signs and symptoms have abated, stabilized, or until abnormal laboratory findings have returned to acceptable or pre-study limits. The final status of the AE will be reported in the participant's medical records and the appropriate eCRF.

Reasons for treatment discontinuation should be classified as follows:

- Death
- Progressive disease
- Toxicity; treatment related or unrelated
- Investigator judgment
- The Investigator may discontinue a participant if, in his/her judgment, it is in the best interest of the participant to do so.
- Noncompliance
- Participant voluntary withdrawal
- A participant may withdraw from the study at any time, for any reason. If a participant discontinues treatment, an attempt should be made to obtain information regarding the reason for withdrawal.
- Sponsor decision.
- Intercurrent illness that prevents further administration of treatment.
- The participant has a confirmed positive serum pregnancy test.
- The participant is lost to follow-up.
- Confirmed radiographic disease progression.
 - *Note:* For unconfirmed radiographic disease progression, please see Section 6.5.
 - *Note:* A participant may be granted an exception to continue on treatment with confirmed radiographic progression if clinically stable or clinically improved, please see Section 6.5. Consent addendum should be obtained to continue on treatment past progression.

- Completed 24 months of uninterrupted treatment with pembrolizumab or 35 administrations of study medication, whichever is later.
 - *Note:* 24 months of study medication is calculated from the date of first dose. Subjects who stop pembrolizumab after 24 months may be eligible for up to one year of additional study treatment if they progress after stopping study treatment provided they meet the requirements detailed in **Section 8.10**.

The End of Treatment and Follow-up visit procedures are listed in **Section 8**. After the end of treatment, each participant will be followed for 30 days for adverse event monitoring (serious adverse events will be collected for 90 days after the end of treatment as described in **Section 10.2**). Participants who discontinue for reasons other than progressive disease will have post-treatment follow-up for disease status until disease progression, initiating a non-study cancer treatment, withdrawing consent or becoming lost to follow-up. After documented disease progression each participant will be followed by telephone for overall survival until death, withdrawal of consent, or the end of the study, whichever occurs first.

6.6.1 Discontinuation of Study Therapy after CR

Discontinuation of treatment may be considered for participants who have attained a confirmed CR that have been treated for at least 24 weeks with pembrolizumab and had at least two treatments with pembrolizumab beyond the date when the initial CR was declared. Participants who then experience radiographic disease progression may be eligible for up to one year of additional treatment with pembrolizumab via the Second Course Phase at the discretion of the investigator if no cancer treatment was administered since the last dose of pembrolizumab, the participant meets the safety parameters listed in the Inclusion/Exclusion criteria, and the trial is open. Participants will resume therapy at the same dose and schedule at the time of initial discontinuation.

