5.2 Exclusion Criteria

Participants will be excluded from this study for the following:

1. Participants who have had chemotherapy, targeted therapies, radiotherapy, or used an investigational device within 2 weeks prior to the first dose of treatment or those who have not recovered from adverse events

- (i.e., \leq Grade 1 or at baseline) due to agents administered more than 2 weeks earlier. Note: Participants with \leq Grade 2 neuropathy are an exception to this criterion and may qualify for the study.
2. Has a diagnosis of immunodeficiency or is receiving systemic steroid therapy or any other form of immunosuppressive therapy within 7 days prior to the first dose of trial treatment.
 3. Has a known history of active TB (Bacillus Tuberculosis).
 4. Hypersensitivity to pembrolizumab or any of its excipients.
 5. Prior severe infusion reaction to cetuximab
 6. Has a known additional malignancy that requires active treatment. Exceptions include basal cell carcinoma of the skin or squamous cell carcinoma of the skin that has undergone potentially curative therapy or in situ cervical cancer.
 7. Has known active central nervous system (CNS) metastases and/or carcinomatous meningitis. Participants with previously treated brain metastases may participate provided they are stable (without evidence of progression by imaging for at least four weeks prior to the first dose of trial treatment and any neurologic symptoms have returned to baseline), have no evidence of new or enlarging brain metastases, and are not using steroids for at least 7 days prior to trial treatment. This exception does not include carcinomatous meningitis which is excluded regardless of clinical stability
 8. Has active autoimmune disease that has required systemic treatment in the past 2 years (i.e. with use of disease modifying agents, corticosteroids or immunosuppressive drugs). Replacement therapy (e.g., thyroxine, insulin, or physiologic corticosteroid replacement therapy for adrenal or pituitary insufficiency) is not considered a form of systemic treatment.
 9. Has known history of, or any evidence of active, non-infectious pneumonitis.
 10. Uncontrolled clinically significant intercurrent illness including, but not limited to, ongoing or active infection, symptomatic congestive heart failure, unstable angina pectoris, unstable cardiac arrhythmia, or psychiatric illness, substance abuse disorders or social situations that would limit compliance with study requirements.

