Grade 3 or 4: 3rd occurrence	
 • Delay infusion one to two weeks • Once symptoms improve, continue dosing and reduce by one further dose level • If there is no improvement in symptoms for ≥ 4 weeks, discontinue cetuximab.
Grade 3 or 4: 4th occurrence	
 • Discontinue cetuximab
Diarrhea	
Grade 1	
 • Continue at same dose level
Grade 2 ²	
 • If anti-motility agents not maximized, maximize supportive care.¹ • If anti-motility agents maximized, hold cetuximab. When symptoms improve to \leq grade 1, resume with dose reduced by one dose level
Grade 3 or 4	
 • Hold cetuximab until adequate resolution • If symptoms improve to grade 1, resume with dose reduced by one dose level • If symptoms do not improve within 2 weeks, permanently discontinue
Respiratory toxicity	
Acute onset or worsening pulmonary symptoms	
 • Interrupt cetuximab dosing
Confirmed ILD	
 • Permanently discontinue cetuximab
Infusion reaction	
 • Reduce the infusion rate by 50% for NCI CTC Grade 1 or 2 and non-serious NCI CTC Grade 3 infusion reactions. Immediately and permanently discontinue cetuximab for serious infusion reactions, requiring medical intervention and/or hospitalization.

18. For patients who find the rash to be intolerable, the dose may be reduced at the investigator's discretion.

19. Additionally refer to 6.3.2. Patients who are receiving additional supportive care measures require close follow-up, minimally within 72 hours by phone and 7 days in clinic.

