8.10 Second Course Phase (Retreatment Period)

Participants who stop cetuximab and pembrolizumab with SD or better may be eligible for up to one year of additional therapy if they progress after stopping study treatment. This retreatment is termed the Second Course Phase of this study and is only available if the study remains open and the subject meets the following conditions:

- **Either**

- Stopped initial treatment with pembrolizumab after attaining an investigator-determined confirmed CR according to RECIST 1.1, and
 - Was treated for at least 24 weeks with pembrolizumab before discontinuing therapy
 - Received at least two treatments with pembrolizumab beyond the date when the initial CR was declared

OR

- Had SD, PR or CR and stopped pembrolizumab treatment after 24 months of study therapy for reasons other than disease progression or intolerability

AND

- Experienced an investigator-determined confirmed radiographic disease progression after stopping their initial treatment with pembrolizumab
- Did not receive any anti-cancer treatment since the last dose of pembrolizumab
- Has a performance status of 0 to 2 on the ECOG Performance Scale (**Appendix B**)
- Meets the safety parameters as detailed in **Section 5.1**
- Female participants of childbearing potential should have a negative serum or urine pregnancy test within 72 hours prior to receiving retreatment with study medication.
- Female participants of childbearing potential should be willing to use 2 methods of birth control or be surgically sterile, or abstain from heterosexual activity for the course of the study through 120 days after the last dose of pembrolizumab and 180 days after the last dose of cetuximab. (Reference **Section 5.1**). Participants of child bearing potential are those who have not been surgically sterilized or have been free from menses for > 1 year.
- Does not have a history or current evidence of any condition, therapy, or laboratory abnormality that might interfere with the participant's participation for the full duration of the trial or is not in the best interest of the participant to participate, in the opinion of the treating investigator.

Participants who restart treatment will be retreated at the same dose and dose interval as when they last received cetuximab and pembrolizumab. Treatment will be administered for up to one additional year.

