Visit requirements are outlined in **5: Schedule of Procedures and Observations for Second Treatment Course**. Both cetuximab and pembrolizumab would restart simultaneously.

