12.4 Safety Analysis

12.4.1 Adverse Event

The frequency of toxicities will be tabulated by maximum grade by preferred term within a patient across all cycles. All participants who receive any study treatment will be considered evaluable for toxicity.

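### For relapse after complete response, Sections 6.6.1 and 8.10 give different Second Course rules, and the restart of both drugs in 8.10 is not reconciled with the permanent cetuximab stops in Table 2

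*Combined protocol and SAP*

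**What the plan says.** Section 6.6.1 covers patients who stop after a confirmed CR. On later radiographic progression they may receive "up to one year of additional treatment with pembrolizumab via the Second Course Phase", at the investigator's discretion, provided that "the participant meets the safety parameters listed in the Inclusion/Exclusion criteria". They resume at the dose and schedule in force when they stopped.

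Section 8.10 defines the Second Course Phase and has two entry routes: the CR route, and stopping pembrolizumab after 24 months with stable disease or better. Both routes require investigator-determined, confirmed radiographic progression. The safety condition reads "Meets the safety parameters as detailed in" Section 5.1, which holds the inclusion criteria. Retreatment is at the dose and interval at which the two drugs were last received, and "Both cetuximab and pembrolizumab would restart simultaneously". Table 5 schedules both drugs.

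Table 2 (Section 6.1.2) instructs sites: "Immediately and permanently discontinue cetuximab for serious infusion reactions, requiring medical intervention and/or hospitalization". It also ends cetuximab for confirmed interstitial lung disease (ILD), for grade 3 or 4 diarrhea that does not improve within 2 weeks, and at a fourth grade 3 or 4 skin event. The skin entry does not use the word permanently, but it offers no restart. Exclusion 5 in Section 5.2 is "Prior severe infusion reaction to cetuximab".

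**The concern.** Two sections govern re-entry for the same CR patient, and they differ on which drugs restart, which eligibility list applies and whether progression must be confirmed. On either route, the instruction to restart both drugs meets a Table 2 rule that may have ended cetuximab for good in that patient, and nothing says which prevails.

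The main stake is patient safety: a site following 8.10 to the letter would re-expose a patient to a drug that the protocol itself had stopped. Consistency is also at stake, because two sites could handle the same patient in opposite ways and both point to the protocol.

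**Working it through.** The plan gives no figure to reproduce here, so the check sets the passages side by side.

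**Step 1: which section governs whom.** The CR route appears in 6.6.1 and again as the first branch of 8.10, with the same minimum of 24 weeks on pembrolizumab and two treatments after CR was declared. For patients who stop at 24 months, the note in Section 6.6 points to 8.10 alone. Section 6.6.1 does not apply to them.

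**Step 2: the two rules for a CR patient.**

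| Item | Section 6.6.1 | Section 8.10 and Table 5 |
|---|---|---|
| Drug(s) named | Pembrolizumab | Cetuximab and pembrolizumab together |
| Eligibility source | Inclusion and exclusion criteria (safety parameters) | Section 5.1, plus a general item resembling exclusion 16 |
| Progression | Radiographic | Radiographic, investigator-determined and confirmed |
| Dose and schedule | As at initial discontinuation | As when both drugs were last received |

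**Step 3: can a patient whose cetuximab was permanently stopped get this far?** Section 6.1 allows pembrolizumab on Day 1 while cetuximab is held for its own toxicity. Continuing after a permanent stop is implied rather than spelled out. Section 12.3 replaces patients in whom a cetuximab infusion reaction makes continuation infeasible, but it does not say that they stop pembrolizumab, and it does not mention the other Table 2 stops.

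**Step 4: does 8.10 screen such a patient out?** Its only intolerability wording concerns stopping pembrolizumab and sits in the 24-month branch. The general item on conditions or abnormalities rests on the investigator's opinion. The eligibility row in Table 5 cites no section, and its footnote gives only timing. No item names a previous permanent stop of cetuximab.

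**Step 5: two CR patients.**
- *Serious cetuximab infusion reaction in course 1.* Under 6.6.1 with exclusion 5 the patient is barred, if a serious reaction counts as a severe one. Under 6.6.1, taking the drug it names and the schedule at discontinuation, the patient receives pembrolizumab only. Under 8.10 and Table 5 both drugs restart, against Table 2.
- *Resolved Grade 2 pneumonitis in course 1.* Table 1 (Section 6.1.1) lets pembrolizumab resume at Grade 1 or less. If the patient later relapses from CR, no specific item in 8.10 bars retreatment, while 6.6.1 with exclusion 9 (history of non-infectious pneumonitis) may.

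**Step 6: effect on the primary efficacy tests.** The Second Course begins only after progression. Best response is recorded up to progression (Section 9.4), and progression is itself the PFS event, so retreatment comes after both outcomes are fixed.

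**The case against.** The best defence is that the sections add up. Section 6.6.1 routes patients through the Second Course Phase, and 8.10 says that the phase is available only if its own conditions are met. A CR patient would then need confirmed progression and also the inclusion/exclusion safety parameters, and a stricter condition in one place is not a contradiction. The eligibility form carries both lists. On drugs, the 8.10 sentence about restarting can be read as timing only, nothing in 8.10 lifts a permanent stop, and 6.6.1 resumes the schedule at discontinuation.

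This is a fair reading of eligibility and progression, but the text does not state it. It does not settle the drugs either. Section 8.10 ties retreatment to the last doses of both agents, Table 5 schedules both, and on the 24-month route there is no 6.6.1 to fall back on.

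Some stronger readings are tempting but unsupported:
- A reader might infer that a 24-month patient with stable disease also faces the three outcomes in Step 5. Section 6.6.1 does not reach that patient, whose only conflict is 8.10 against Table 2.
- A reader might infer that 8.10 drops most of Section 5.2. Section 6.2 carries the medications and vaccinations barred by the exclusion criteria into the ongoing trial. Section 6.2.2 extends its prohibitions, including live vaccines and most systemic steroids, to retreatment after CR relapse.
- A reader might infer that any cetuximab stop for toxicity leads to a bar. That is clearest for a severe infusion reaction and arguable for ILD through exclusion 9. No exclusion names rash or diarrhea as a reason.
- The condition "Did not receive any anti-cancer treatment since the last dose of pembrolizumab" might be taken to disqualify anyone given study cetuximab on Days 8 and 15 of the last cycle. That would empty a phase opened to patients stopping both drugs, and Section 6.6 elsewhere speaks of non-study cancer treatment.
- Section 12.4.1 ("The frequency of toxicities will be tabulated by maximum grade by preferred term within a patient across all cycles") might be thought to require a separate second-course table. It does not say whether second-course cycles count, and a split is a preference, not a correction.

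**Conclusion.** The point holds in this limited form and should be fixed. For CR patients the two sections give different rules on drugs, eligibility and progression. On both routes, the 8.10 restart of both drugs is not reconciled with the Table 2 stops. The text allows opposite handling of the same patient, but it does not establish that any site would in fact re-expose one.

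The number affected is small. The documents give no expected count. Assuming that 0 to 4 of the 42 patients reach a second course (0% to 9.5%, since 4/42 = 0.095), only those with a first-course toxicity of the kind described are affected. The conclusion does not depend on that range. It does rest on two readings: that pembrolizumab may continue after a permanent cetuximab stop, which Section 6.1 implies, and, for the outcomes involving a bar, that exclusions 5 and 9 count as safety parameters, a term that the protocol does not define. The objective response and 6-month PFS tests are essentially untouched. The weight of the point is retreatment safety and consistency between sites.

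**What to change.** Reconcile 6.6.1, 8.10, Table 2 and Table 5. Keep one list of entry conditions in 8.10 and have 6.6.1 and the eligibility row of Table 5 refer to it. The list should state:
- whether Section 5.2 applies as well as 5.1 and, if only in part, which items count as safety parameters;
- whether progression must be confirmed;
- how the restart instruction applies to a patient with a permanent discontinuation of one drug under Table 1 (Section 6.1.1) or Table 2.

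The clinical choice on each is the sponsor's. As an optional clarification, the clause on intervening cancer treatment could say that it means non-study treatment, if that is the intent.

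The cost is a short protocol amendment. It adds no patients, procedures or analyses.
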